- Compare the tumor mutation burden and alterations in DNA repair genes in the pre and post Durvalumab urothelial bladder cancer samples

Study Design:

This is a multicenter, open-label, Phase 2 study of Durvalumab to evaluate its antitumor activity for BCG refractory urothelial carcinoma in situ (CIS) of the bladder. Durvalumab will be given every 4 weeks at 1500 mg IV for total of 12 months. Cystoscopy with biopsy and TURBT (if indicated) will be performed at baseline, and every 3 months during the 12 months treatment period and then every 4 months in the 12 month surveillance period. Of note, cystoscopy at baseline, month 6, and 24 will be performed in the operating room with mapping biopsies. Patients will be off study if any of the biopsies document muscle invasive (T2 or above) urothelial carcinoma. Patients will also be off study if their month 6, 12, 16, 20, biopsies show persistent (month 6) or recurrent CIS or invasive (T1 or above) urothelial carcinoma. Otherwise, patients will remain on study until after the month 24 biopsy.

Number of Centers: 2-3 centers in North America

Number of Subjects: 34

Study Population:

Adult male or female subjects with pathologically confirmed urothelial carcinoma in situ (CIS) of the bladder that is refractory to BCG (see inclusion criteria 2).

Inclusion Criteria:

1. Age \geq 18 years at the time of screening with life expectancy of \geq 2 years
2. Must have pathologically confirmed urothelial carcinoma in situ (CIS) of the bladder that meet one of the following criteria:
 1. Persistence of high-grade CIS at 6 months following an adequate course of BCG; OR
 2. Stage/grade progression at 3 months after induction BCG; OR
 3. Recurrence of high-grade CIS after achieving a disease-free state (i.e., CR) following induction of an adequate course of BCG that occurs $<$ 9 months after the last exposure to BCG; OR
 4. Persistent CIS noted on the bladder biopsies within 3 months of completing at least 2 induction BCG (minimum of five weekly instillations).
- An adequate course of BCG should be defined as at least one course of induction (minimum of five weekly instillations) and one maintenance (two of three instillations) in a 6 months period, with an exception for any patient with grade/stage progression after induction BCG (minimum of five weekly instillations).
3. ECOG performance status of 0-1.

4. Adequate organ and marrow function, as defined as:

- Hemoglobin ≥ 9.0 g/dL,

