If the infusion takes longer than 60 minutes then blood pressure and pulse measurements should be collected every 30 minutes (±5 minutes) and as described above or more frequently if clinically indicated.

^e ECG during screening and at Day1 –baseline. There after as clinically indicated. Baseline and abnormal ECG at any time in triplicate others single. 1 ECG is needed while on treatment>>, and as clinically indicated. ECGs should be taken within an hour prior to the start of the infusion and at least one time point 0 to 3 hours after the infusion.

^f If screening laboratory assessments are performed within 3 days prior to Day 1 they do not need to be repeated at Day 1. Results for safety bloods must be available and reviewed before commencing an infusion. Gamma glutamyltransferase tested at Screening, Day 1 and as clinically indicated.

- g Free T3 and free T4 will only be measured if TSH is abnormal. They should also be measured if there is clinical suspicion of an adverse event related to the endocrine system.
- h Urinalysis performed at Screening, Day 1, every 4 weeks and as clinically indicated.
- i Coagulation tests: prothrombin time, APTT and INR – only performed at Screening and as clinically indicated.
- j Cystoscopy at baseline, week 26/month 6, and week 104/month 24 will be performed in the operating room with mapping biopsies. The mapping biopsy at baseline can be waived if the subject has a cystoscopy within 8 weeks, which documented recurrent or persistent CIS without evidence of muscle invasive urothelial bladder cancer. After month 3, 9, 12, 16 and 20 cystoscopy, a biopsy will be performed at the discretion of the Urologist.
- k Chest X-ray and CT (preferably with IV contrast) are collected during screening (for baseline) to rule out metastatic disease and secondary malignancy, Due to the low risk of metastasis with CIS of bladder, repeat imaging studies will not be indicated until cancer in the bladder has progressed to the muscle invasive stage. At this point subjects will be off study due to disease progression

Clinical Study Protocol

Investigational Drug Substance: MEDI4736 Durvalumab (Medi4736)

Study Number MCC 18788/MCC18788/ESR-15-11326

Edition Number 1.9.4

Date 10/08/2018

TABLE OF CONTENTS

PAGE

SYNOPSIS.....	3
SCHEDULE OF ASSESSMENTS.....	9
TABLE OF CONTENTS.....	13
ABBREVIATIONS AND DEFINITION OF TERMS.....	19
1. INTRODUCTION	24
1.1 Disease Background.....	24
1.2 Durvalumab Background	25

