1. INTRODUCTION

1.1 Disease Background

Bladder cancer is the fifth most common cancer in the United States. Approximately 74,690 new cases (56,390 men and 18,300 women) and 15,580 deaths (11,170 men and 4,410 women) from bladder cancer would occur in the United States in 2014. Nearly 75% of newly diagnosed bladder cancers are non-muscle invasive bladder cancer (NMIBC) or “superficial bladder cancer”. CIS is a flat high-grade noninvasive urothelial carcinoma (UC) that has a high propensity for invasion and metastasis. It may occur in isolation or with a synchronous UC. Other than bladder, it could also occur in urothelium lines upper tract, prostatic and penile urethral. The incidence of CIS of bladder is about 14-19% based on the published data with multiple bladder biopsies.

Intravesical BCG remains the most effective treatment for non-muscle invasive bladder cancer. Its efficacy is attributed to immune response induced by BCG, which tends to wane over time. BCG refractory bladder cancer is commonly defined as recurrence after 2 induction courses of BCG, or recurrence within 6 months of completing induction and maintenance phase of BCG. Unlike TURBT for Ta and T1 UC, CIS cannot be completely resected by biopsy. Standard therapy for BCG refractory CIS is radical cystectomy. For patients who are unsuitable for or refuse radical cystectomy, one approach would be enhancing the protective immunity induced by intravesical BCG by adding agents like interferon- α (Lam et al, 2003). Alternative approaches would be intravesical valrubicin or intravesical gemcitabine. Although intravesical valrubicin is the only FDA approved salvage agent, its complete response rate was only 18% at 3 months and 4% at year 2 in BCG refractory or intolerant CIS (Dinney et al, 2013). There is an unmet need to develop more effective therapy for BCG refractory CIS of bladder. Based on the report of the FDA and AUA joint workshop in 2013, an agent with an initial CR rate of 40-50% at month 6 and a durable response rate of at least 30% would be considered meaningful for BCG refractory CIS (Jarow et al, 2014).

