2.2 Secondary objective(s)

1. To evaluate whether Durvalumab can improve the complete response rate at year 2 to 30% or above based on the week 104 mapping biopsy in BCG refractory CIS urothelial bladder cancer
2. To assess the safety and tolerability of Durvalumab at 1500 mg Q4W IV infusion for 12 months for BCG refractory CIS urothelial bladder cancer

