3. STUDY DESIGN

3.1 Overview of study design

This is a multicenter, open-label, Phase 2 study of Durvalumab to evaluate its antitumor activity for BCG refractory urothelial carcinoma in situ (CIS) of the bladder. We use a Simon's two-stage design (Simon, 1989) based on the optimal two-stage designs and admissible designs (Jung et al. 2004) for Phase II single arm clinical trials. In the first stage of this study plan, 13 patients will be accrued. If there are 3 or fewer responses in these 13 patients, the study will be stopped. Otherwise, 21 additional patients will be accrued for a total of 34. Durvalumab will be given every 4 weeks at 1500 mg IV for total of 12 months/13 doses. Cystoscopy with mapping biopsy and TURBT (if indicated) will be performed at

Clinical Study Protocol

Investigational Drug Substance: MEDI4736 Durvalumab (Medi4736)

Study Number MCC 18788/MCC18788/ESR-15-11326

Edition Number 1.9.4

Date 10/08/2018

baseline, month 6, and 24. Urine cytology with UroVysion test will be performed at baseline, month 6, and 24. Patients will be off study if any of the biopsies documented muscle invasive (T2 or above) urothelial carcinoma. Patients will also be off study if their month 6, 12, 18 biopsies showed persistent (month 6) or recurrent CIS or invasive (T1 or above) urothelial carcinoma. Otherwise, patient will remain on study until after the month 24 biopsy.

Historical controls will be used to assess the efficacy of Durvalumab. For exploratory analysis on PD-L1 expression, PD-L1 IHC will be performed with the SP263 antibody developed by Ventana. IHC positivity (either on tumor cells and/or infiltrating immune cells) will be assessed on the available mapping biopsy and or TURBT samples at time points defined in SCHEDULE OF STUDY ASSESSMENT.

Data Monitoring Committee (DMC) at Moffitt Cancer Center will monitor this phase 2 study initiated by Moffitt's investigator.

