9. DISEASE EVALUATION AND METHODS

The response to immunotherapy may differ from the typical responses observed with cytotoxic chemotherapy including the following (Wolchok et al 2009, Nishino et al 2013):

- Response to immunotherapy may be delayed
- Response to immunotherapy may occur after PD by conventional criteria
- The appearance of new lesions may not represent PD with immunotherapy
- SD while on immunotherapy may be durable and represent clinical benefit.

Based on the above-described unique response to immunotherapy, subjects with persistent CIS at the month 3 bladder biopsy will continue to receive Durvalumab until the month 6 bladder biopsy documented persistent CIS or progression to the muscle invasive stage. Durvalumab will be discontinued and subjects will be off study if invasive bladder cancer (T1 or above) is documented in any of the bladder biopsies. Due to the nature of CIS of bladder, RECIST 1.1 or irRECIST will not be applicable to response assessment.

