9.1.1 Pathological response

The absence of CIS of bladder on the mapping biopsies after pathological review would be considered complete response to treatment. Subjects who are withdrawn from durvalumab treatment for reasons other than confirmed progression to the muscle invasive stage will continue to have objective tumor assessments (see Appendix C).

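### Year 2 complete response is a single week 104 reading with no sustained-response condition, so CIS found at month 9 but absent at week 104 counts towards a 30% target taken from a durability benchmark

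*Combined protocol and SAP*

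**What the plan says.** - **Endpoint.** Section 2.2 sets out to "improve the complete response rate at year 2 to 30% or above based on the week 104 mapping biopsy". The efficacy assessments in the synopsis also read year 2 response from the year 2 mapping biopsy.
- **Definition of response.** Section 9.1.1: "The absence of CIS of bladder on the mapping biopsies after pathological review would be considered complete response to treatment". It adds no condition on earlier or intervening biopsies.
- **Where mapping biopsies fall.** Footnote j of the schedule of assessments: "Cystoscopy at baseline, week 26/month 6, and week 104/month 24 will be performed in the operating room with mapping biopsies". The same footnote leaves biopsies at months 3, 9, 12, 16 and 20 to the urologist's judgement.
- **Origin of the 30%.** Section 1.1, reporting a regulatory workshop: "a durable response rate of at least 30% would be considered meaningful for BCG refractory CIS". Section 1.4 repeats it as the rationale.
- **Off-study rule, synopsis.** "Patients will also be off study if their month 6, 12, 16, 20, biopsies show persistent (month 6) or recurrent CIS"; then "Otherwise, patients will remain on study until after the month 24 biopsy".
- **Off-study rule, section 3.1.** "Patients will also be off study if their month 6, 12, 18 biopsies showed persistent (month 6) or recurrent CIS".
- **Invasive disease, section 9.** "subjects will be off study if invasive bladder cancer (T1 or above) is documented in any of the bladder biopsies". For CIS alone, section 9 speaks only to months 3 and 6.
- **Analysis.** Section 11.2.2 makes the month 24 analysis descriptive. No year 2 sample size, power or decision rule is given.

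**The concern.** A target expressed as durable response is being compared with a rate read at one time point. A subject who responded, relapsed with biopsy-proven CIS and was clear again at week 104 has not had a continuous response, but the definition does not separate that subject from one who stayed clear throughout.

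The off-study rules remove most such subjects before week 104, but not all, and they make the score depend on the visit at which the relapse is found. The year 2 rate is the only secondary efficacy endpoint and the only planned evidence on durability. Any misclassification of this kind adds responders and never removes them.

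**Working it through.** **The plan's own figures.** The documents give no calculation for year 2 to reproduce. The month 6 design (13 then 34 subjects, stop at 3 or fewer, 10 or more needed at the end) reproduces at type I error 0.0473 and power 0.8031. This point does not touch it.

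**Step 1: which relapses are open.** Between week 26 and week 104 the schedule has cystoscopy at weeks 38, 52, 68 and 86 (months 9, 12, 16 and 20).

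| CIS found at | Synopsis list (6, 12, 16, 20) | Section 3.1 list (6, 12, 18) |
|---|---|---|
| Month 9 | stays on study | stays on study |
| Month 12 | off study | off study |
| Month 16 | off study | stays on study |
| Month 20 | off study | stays on study |

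The month 18 visit named in section 3.1 is not in the schedule.

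**Step 2: two records scored literally.** Both subjects are CIS-free at week 26.
- CIS on a month 9 biopsy, no CIS at later assessments, CIS-free at week 104: year 2 responder.
- CIS on a month 12 biopsy: off study, so no on-study week 104 biopsy and no year 2 response to score.

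The same kind of relapse gets a different outcome according to the visit.

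**Step 3: upper bound on size.** Assumptions: 34 subjects; 40% response at month 6, so 0.40 × 34 = 13.6 responders; constant relapse hazard bringing 40% down to 30% at month 24; every open relapse biopsied, and every one CIS-free at week 104.

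- Hazard: h = −ln(0.30/0.40)/18 = 0.0160 per month.
- Share of responders with relapse first detectable between visits at a and b months: exp(−h(a−6)) − exp(−h(b−6)). This gives 0.047 at month 9, 0.045 at month 12, 0.056 at month 16 and 0.053 at month 20.
- Synopsis list (month 9 only): 0.047 × 13.6 = 0.64 subject; 0.40 × 0.047 = +1.9 points.
- Section 3.1 list (months 9, 16 and 20): 0.047 + 0.056 + 0.053 = 0.156; × 13.6 = 2.1 subjects; 0.40 × 0.156 = +6.2 points.

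The documents give no rate of relapse followed by clearance, so the lower bound is zero under either list.

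**Step 4: what that does to the 30% comparison.** On an assumed denominator of 34, 10/34 = 29.4% and 11/34 = 32.4%, so one subject separates missing 30% from meeting it. With an assumed true durable rate of 27.5%, the binomial probability of 11 or more of 34 is 0.32. Under the synopsis list, if half of the month 9 relapses are clear at week 104 (+0.9 points) it is 0.37; if all are (+1.9 points) it is 0.41. Values of 0.47 (+3 points) or 0.62 (+6 points) need the section 3.1 list.

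**The case against.** **The off-study rule already does most of the work.** This stands. A reader might infer that any CIS between week 26 and week 104 can end as a year 2 success. The synopsis does not allow that: CIS at month 12, 16 or 20 ends participation. A month 9 relapser must also show no CIS at those later visits to reach week 104. The months 16 and 20 gap exists only on the section 3.1 list, which conflicts with the synopsis and with the schedule.

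**Persistent CIS at month 6 is not a clear route to year 2 credit.** A reader might infer that a subject with CIS at week 26 after fewer than 6 doses could still be credited, because section 6.1 follows such subjects to month 24. Both off-study lists remove CIS at month 6 without a dose exception, and section 11.1.2 keeps these subjects out of the efficacy set. The texts conflict, and this point does not rest on that case.

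**Larger effects are not supported.** The valrubicin figures in section 1.1 (18% at 3 months, 4% at year 2) imply a hazard of −ln(0.04/0.18)/21 = 0.0716 per month, hence 19.3% of responders relapsing by month 9 and up to +7.7 points. That hazard also implies a durable rate of 0.40 × exp(−0.0716 × 18) = 11.0%. Even at 18.7% after full inflation, the chance of 11 or more of 34 is 0.04, so 30% would almost always be missed anyway.

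**The endpoint is descriptive, and the benchmark is undefined.** Both are true. The 11-of-34 cut is an illustration, not a rule in the plan. The documents do not say how the workshop defined durable response, and the endpoint is named as a rate at year 2. What remains is that section 2.2 sets a numerical target whose only stated source is a durability benchmark, while the scoring contains no durability condition.

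**Mapping biopsies are at least uniform.** Also true. Section 1.5 speaks of mapping biopsy every 3 months, but footnote j limits it to three time points and leaves the others to judgement. A numerator that uses interim biopsies inherits that variation.

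**Conclusion.** The point holds in a narrow form. Year 2 complete response has no sustained-response condition. Under the synopsis list, a month 9 relapse that is absent at week 104 is credited as a response; under the section 3.1 list, relapses found at months 16 and 20 can be too. The two lists contradict each other and must be reconciled.

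The size is between zero and about 0.6 of 34 subjects (+1.9 points) with the synopsis list, or about 2.1 subjects (+6.2 points) with the section 3.1 list. These upper ends rest on 40% response at month 6, a constant hazard to 30% at month 24, biopsy of every open relapse and clearance of every one by week 104. The direction is upward only. The documents do not support describing this as a large or general inflation of the year 2 rate, and the primary analysis is unaffected. The change is worth making because it is cheap and because one subject can separate a rate below 30% from one above it.

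**What to change.** In the synopsis efficacy assessments, section 2.2 and section 9.1.1, define year 2 complete response as all three of:

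1. no CIS on the week 26 mapping biopsy;
2. no CIS on the week 104 mapping biopsy;
3. no CIS on any bladder biopsy taken between them.

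Report the week 104 point-in-time rate beside it as a labelled supportive figure. Separately, reconcile the off-study lists in the synopsis and section 3.1 with each other and with the schedule, and state how CIS at month 9 is handled. The scoring definition works whichever way that is settled, and it changes neither treatment nor off-study rules.

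The cost is wording in three places, with no added procedure or subject. Downsides to state in the plan:
- the year 2 rate may be slightly lower;
- a subject who relapsed and then cleared is no longer credited;
- because biopsies at months 9, 12, 16 and 20 are discretionary, relapses that were not biopsied stay undetected, and detection may differ between centers.

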2.3 Exploratory objective(s)

1. Correlate PD-L1 expressions in urothelial carcinoma, tumor infiltrating T cells, mononuclear cells in bladder biopsy or TURBT samples with response to Durvalumab
2. Correlate chromosomal abnormalities detected by UroVysion urine test with response to Durvalumab
3. Compare the tumor mutation burden and alterations in DNA repair genes in the pre and post Durvalumab urothelial bladder cancer samples

3. STUDY DESIGN

3.1 Overview of study design

This is a multicenter, open-label, Phase 2 study of Durvalumab to evaluate its antitumor activity for BCG refractory urothelial carcinoma in situ (CIS) of the bladder. We use a Simon's two-stage design (Simon, 1989) based on the optimal two-stage designs and admissible designs (Jung et al. 2004) for Phase II single arm clinical trials. In the first stage of this study plan, 13 patients will be accrued. If there are 3 or fewer responses in these 13 patients, the study will be stopped. Otherwise, 21 additional patients will be accrued for a total of 34. Durvalumab will be given every 4 weeks at 1500 mg IV for total of 12 months/13 doses. Cystoscopy with mapping biopsy and TURBT (if indicated) will be performed at

Clinical Study Protocol

Investigational Drug Substance: MEDI4736 Durvalumab (Medi4736)

Study Number MCC 18788/MCC18788/ESR-15-11326

Edition Number 1.9.4

Date 10/08/2018

baseline, month 6, and 24. Urine cytology with UroVysion test will be performed at baseline, month 6, and 24. Patients will be off study if any of the biopsies documented muscle invasive (T2 or above) urothelial carcinoma. Patients will also be off study if their month 6, 12, 18 biopsies showed persistent (month 6) or recurrent CIS or invasive (T1 or above) urothelial carcinoma. Otherwise, patient will remain on study until after the month 24 biopsy.

Historical controls will be used to assess the efficacy of Durvalumab. For exploratory analysis on PD-L1 expression, PD-L1 IHC will be performed with the SP263 antibody developed by Ventana. IHC positivity (either on tumor cells and/or infiltrating immune cells) will be assessed on the available mapping biopsy and or TURBT samples at time points defined in SCHEDULE OF STUDY ASSESSMENT.

Data Monitoring Committee (DMC) at Moffitt Cancer Center will monitor this phase 2 study initiated by Moffitt's investigator.

3.2 Study schema

Clinical Study Protocol

[figure not shown]
Investigational Drug Substance: MEDI4736 Durvalumab (Medi4736)

Study Number MCC 18788/MCC18788/ESR-15-11326

Edition Number 1.9.4

Date 10/08/2018

Figure 1. Study flow chart

3.3 Study Oversight for Safety Evaluation

DMC at Moffitt Cancer Center will monitor this phase 2 study initiated by Moffitt's investigator. The study will be stopped early if there are 3 or fewer responses in the first 13 patients in the stage I of Simon 2 stage design. The study will also be stopped early if 3 or more subjects of the first 10 subjects developed SAEs attributed to Durvalumab.

